Our preliminary data demonstrate that monocyte transformation to foam cell begins in the circulation in response to increased inflammation and oxidative stress that activates lipid uptake and/or de novo synthesis. These activated-lipid laden monocytes will then migrate to the subendothelium and uptake more lipids and progress to form the atherosclerotic lesion. This observation represents an early stage in atherogenesis and can be used, therefore, as an early screening test for vascular disease. Other leucocytes, including T-cells and B-cells, are also recruited to the injury site and participate in the process of plaque formation. Determination of intracellular levels monocytes and lymphocytes, therefore, represents a direct and early marker of monocyte/macrophage activation level and the process of foam cell formation and therefore, the risk for atherosclerosis and vascular disease. The current proposal provides a method for the determination of post cream challenge levels of intracellular lipids in monocytes as a mechanistic model for vascular disease.

Significance of the Study

1. Clinical relevance. Since the formation of the foam cell is potentially important in atherogenesis, it would be important to determine whether drugs that lower LDL cholesterol and atherogenic risk decrease formation of these foam cells.
2. Mechanistic and biological/pathological significance. The confirmation of our preliminary data in a larger study is important since these data provide the first evidence that the formation of the foam cell may occur in circulation and that the monocyte may get loaded with lipid after every fatty meal. This may potentially contribute to atherogenesis. This study may provide a model to study novel mechanisms of action of lipid lowering drugs.

Study Sample:

This will be a double blind, prospective study conducted in 20 qualifying volunteers. Subjects will be recruited from the hospital and university. All subjects will sign a written informed consent approved by the institutional review board of SUNY at Buffalo. Women and members of minority groups will be encouraged to participate in this study and efforts will be made to recruit subjects from these groups.

Subject Assignment:

Experiments will be carried out in obese subjects. There will be 2 groups in the study:-

Group 1 will receive Simvastatin 40 mg and Ezetimibe 10 mg daily combination pill (Vytorin) for 6 weeks

Group 2 will receive a matching placebo pill for 6 weeks

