Randomization:

Subjects will be randomized to 2 groups with 10 patients in each using a computer generated randomization chart.

Group 1 will be getting vytorin 40/10 mg daily for 6 weeks

Group 2 will receive placebo daily for 6 weeks.

Inclusion Criteria for all groups:

- Age: 18 to 65 years of age.
- Obese (BMI \geq 30 kg/m²)
- LDL cholesterol of \geq 100 mg/dl
- Subject will be available for duration of the study and willing to comply with all study requirements
- Written and informed consent signed and dated
- Not taking any vitamins or antioxidants

Exclusion Criteria:

- Currently using anti-hyperlipidemic therapies
- Triglycerides >500 mg/dl.
- Myocardial infarction, angioplasty/stent placement or coronary artery bypass surgery in the past 6 months
- Patient on chronic use of non-steroidal anti-inflammatory drugs or steroids
- Hepatic disease
- Renal impairment
- History of drug or alcohol abuse
- Participation in any other concurrent clinical trial
- Use of an investigational agent or therapeutic regimen within 30 days of study.
- Smoker
- Pregnancy
- Premenopausal women who are not on birth control pills and have not had a hysterectomy or tubal ligation
- Anemia with hemoglobin <12 g/dl

RECRUITMENT OF SUBJECTS:

The recruitment into the study will be carried out by the following methods:

1. Patients for the Diabetes-Endocrinology Center of WNY Clinic
2. Diabetes-Endocrinology Center of WNY - Research Division - Recruitment Database

Accrual Rate: On an average, we plan to recruit 1 patient per week.

All subjects will have completed the following procedures prior to participating in the study.

1) Medical History;

2) Physical Exam

3) Informed consent

4) Baseline lab draws to measure CBC, SMA and lipid profile. All labs will be drawn in the fasting state in the morning before 10am.

Informed Consent

Study process and required visits will be explained to patient in lay terms. All subjects will be asked to sign a consent form approved by IRB and a copy given to all subjects.

STUDY PROCEDURES

Subjects will be randomized to receive Vytorin or matching placebo for 6 weeks.

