Visit 1 at week 0: Subjects will arrive after having fasted (10 hour) overnight. A fasting blood sample will be taken, followed by cream challenge and blood sample will be drawn 1, 2, 3 and 5 hours after the cream challenge. **Cream challenge:** Subjects will be given 100 mL of dairy cream (gourmet heavy whipping cream, Land 'O' Lakes Inc., Arden Hills, MN) to be consumed over 10 minutes. This preparation of dairy cream has 33 g fat (300 Calories) per 100 mL.

Subjects will then be given a supply of their drug to be taken once a day at bedtime.

Visit 2 at week 3: Subject will come fasting for a short visit for a blood draw at 4 weeks.

Visit 3 at Week 6: A fasting blood sample will be taken, followed by cream challenge same as the 1st visit and blood sample will be drawn at 1, 2, 3 and 5 hours after the challenge. Subjects will then be discharged from the study.

COMPENSATION FOR PARTICIPATION:

To help defray the costs of your participation, you will receive \$150.00 for completing the entire study. In the event that you do not complete the entire study, you will receive \$60.00 at Visit 1 and Visit 3 each, and \$30 for Visit 2. You will not be paid for the screening visit. . Please be aware that occasionally additional visits are

required, for safety evaluations or to repeat blood test, and that these visits are not a part of the 3 required visits. There will be no additional compensation for extra visits.

METHODS:

- 1) **MNC and PMN isolation by Ficoll-hyque method:** Blood samples will be collected in Na-EDTA as an anticoagulant. Three and a half mL of anticoagulated blood sample are carefully layered over 3.5 mL of PMN medium (Cedarlane Laboratories, Hornby, ON). Samples are centrifuged and at the end of the centrifugation, two bands separate out at the top of the RBC pellet. The top band consists of MNC, while the bottom consists of PMN. The MNC band is harvested and washed twice with Hank's balanced salt solution (HBSS). This method provides yields greater than 95% pure PMN and MNC suspensions.
- 2) **Monocytes isolation by magnetic beads.** Monocytes will be isolated from MNC fraction by magnetic beads coated with CD14 antibodies (Maltyni Biotec, Auburn, CA) .

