Statistical analysis will be carried out using SPSS and SigmaStat software (Jandel Scientific, CA). All data will be expressed as mean \pm S.E of arbitrary units and percent change is calculated from the means. To evaluate similarity between the study groups, baseline values for subject's demographics will be compared using appropriate parametric and non-parametric tests based upon the nature of the data. To account for the anticipated wide inter-patient variability, baseline measures will be standardized to 100%. All subsequent values will be reported as the percent change from the baseline value. Comparisons for each endpoint will be made using repeated measures ANOVA.

The primary endpoint of the study is to evaluate the change in intracellular lipids in MNCs following cream challenge before and after Vytorin therapy for 6 weeks. Our preliminary studies have shown an increase of 70 \pm 24% in intracellular lipids staining following cream intake in normal subjects. Assuming approximately a 25% decrease in the cream induced intracellular lipid accumulation, a sample size of 20 subjects per group should provide adequate power ($\beta = 0.8$) to detect a statistically significant difference ($\alpha = 0.05$), provided the standard deviation of the residuals is not equal to or greater than the mean difference.

Secondary endpoints: We will measure markers of monocyte activation including CD68 and PECAM expression as well as the activity and the expression of pro-inflammatory transcription factor NF- κ B and its activating protein, IKK β , the expression of pro-inflammatory NF- κ B-regulated genes, TLR-4, and SOCS-3 and oxidative stress in monocytes following cream challenge before and after Vytorin (simvastatin and ezetimibe). The decrease in intracellular lipids before and after combination of the Simvastatin and Ezetimibe will also be analyzed.

Data Safety Monitoring Plan:

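### The 0.8 power is stated for 20 subjects per group, but the trial randomises 10 per group, and the powered contrast is not made clear

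*Combined protocol and SAP*

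**What the plan says.** Three statements in the combined protocol and SAP bear on sample size:

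- Study Sample: "This will be a double blind, prospective study conducted in 20 qualifying volunteers".
- Randomization: "Subjects will be randomized to 2 groups with 10 patients in each using a computer generated randomization chart".
- 9) Data Analysis, primary endpoint paragraph: "a sample size of 20 subjects per group should provide adequate power". The power is 0.8 (written as beta), alpha is 0.05, and the condition is "provided the standard deviation of the residuals is not equal to or greater than the mean difference".

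The effect assumed is a decrease of about 25% in the cream-induced lipid accumulation. The pilot figure is a rise of 70 ± 24% in normal subjects.

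The same paragraph words the primary endpoint as the "change in intracellular lipids in MNCs following cream challenge before and after Vytorin therapy for 6 weeks" and does not mention placebo. Aim 1.1 in Specific Aims refers to Vytorin or placebo, and the design has a randomised, double-blind placebo group. On method, the section says only "Comparisons for each endpoint will be made using repeated measures ANOVA". It names no factor, interaction or time point.

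**The concern.** The power statement describes a trial of 40 subjects, and the plan is for 20. This is the document's only sample-size justification, so the planned trial has none of its own unless the figure happens to carry over.

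The contrast matters as much as the number. A before-after test within one group and a comparison of change between two groups have different power at the same size. If the stated 0.8 is read as applying to the randomised comparison, a non-significant Vytorin-placebo result could be taken as evidence against an effect when the trial may have had little chance of detecting one. The recruiting team also has two conflicting targets, 20 or 40 subjects.

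**Working it through.** **Inputs from the plan.** Power 0.8, alpha 0.05, 20 per group (Data Analysis); 10 per group (Randomization); residual SD below the mean difference (Data Analysis); pilot rise 70 ± 24%; decrease of about 25%; four post-challenge samples (Study Procedures).

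**Not in the plan, so assumed.** A two-sided test; a two-sample t-test on one change value per subject; the proviso's SD taken as the SD of that change.

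**Formula.** Let d = difference / SD. Two-sample power comes from the noncentral t distribution with 2n − 2 degrees of freedom and noncentrality d × √(n/2), for n per group. The proviso means d > 1.

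**The plan's own figure.** With n = 20 and d = 1, noncentrality is √10 = 3.16 and power is 0.869. Power rises as the SD falls, so under this test the proviso secures at least 0.8 at 20 per group. The stated pair (20 and 0.8) is met as a lower bound but not reproduced exactly: 17 per group would suffice at d = 1.

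**The trial as randomised.** With n = 10 and d = 1, noncentrality is √5 = 2.24.

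| SD / difference | Power, 10 per group | Power, 20 per group |
|---|---|---|
| 1.00 (limit, excluded by the proviso) | 0.562 | 0.869 |
| 0.95 | 0.605 | 0.900 |
| 0.90 | 0.652 | 0.928 |
| 0.80 | 0.753 | 0.971 |
| 0.75 | 0.805 | 0.984 |

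For 80% power with 10 per group, d must be 1.325, so SD / difference is at most 1 / 1.325 = 0.755. With 20 per group, d need only be 0.909 (ratio 1.10). One-sided with 10 per group, 80% needs d = 1.156 (ratio 0.865), and power at the limit is 0.694.

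**In the plan's units.** The 25% may mean 25 points, or 25% of the 70-point rise (0.25 × 70 = 17.5 points). For 80% power with 10 per group, the SD of the change must be at most 25 / 1.325 = 18.9 points or 17.5 / 1.325 = 13.2 points.

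**What the pilot ± 24 can tell us.** It is not labelled SD or S.E., and the plan's reporting convention is mean ± "S.E of arbitrary units and percent change is calculated from the means". If 24 is the SD of the response to one challenge, the SD of the before-after change is 24 × √(2(1 − ρ)), where ρ is an unstated within-subject correlation:

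| ρ (assumed) | SD of change | Power, 25 points, 10 per group | Power, 17.5 points, 10 per group |
|---|---|---|---|
| 0.3 | 28.4 | 0.46 | 0.26 |
| 0.5 | 24.0 | 0.60 | 0.34 |
| 0.7 | 18.6 | 0.81 | 0.51 |

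Four of these six cells fall outside the proviso as read here (28.4 against 25, and all three SDs against 17.5). They show how far the answer moves with the unstated inputs; they are not estimates of the trial's power. If 24 is an S.E., the SD is larger and power is lower.

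**Repeated measures.** Suppose instead that the proviso's SD is that of a single residual, that residuals are independent with SD equal to the difference, and that noise in the fasting value is ignored. A before-after change averaged over m time points then has SD √(2/m) times the difference.

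- m = 1: d = 0.707; power 0.32 with 10 per group, 0.59 with 20.
- m = 4: d = 1.414; power 0.85 with 10 per group, 0.99 with 20.

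**Within-group alternative.** A paired two-sided t-test in 10 subjects with SD equal to the difference has noncentrality √10 on 9 degrees of freedom, and power 0.803.

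**The case against.** The best defence is that the sentence contains a slip. If 20 per group should read 20 in total, and the contrast is the before-after change that the endpoint wording describes, the paired calculation for 10 Vytorin subjects gives 0.803 exactly at the proviso's boundary. On that view the plan never claimed 0.8 against placebo. The reading is plausible, but the text does not state it. The reference to groups, the placebo arm and Aim 1.1 all make the between-group reading natural too, so the contrast is at best ambiguous. The slip would still need correcting, and the randomised comparison would be left with no power basis.

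The second defence is that the planned analysis is a repeated measures ANOVA, not a two-sample t-test, and Visit 3 repeats Visit 1's schedule: "blood sample will be drawn at 1, 2, 3 and 5 hours after the challenge". Averaging over those samples could give 85% with 10 per group. This stands as a possibility, and it is why the trial cannot be called underpowered outright. It rests on independent residuals and a noise-free fasting value, both optimistic, and the plan does not say that the samples will be averaged. The same model at one time point gives 32%.

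It is also fair that the 56% limit belongs to one test and one reading of the proviso. It is not a floor across all models.

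**Conclusion.** The power statement is wrong as written for this trial. It is tied to 20 per group, the design has 10, and nothing reconciles them. That contradiction needs no assumption.

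The size of the consequence is conditional. Under a two-sided two-sample t-test on the change, the plan's SD condition secures about 87% with 20 per group but only about 56% with 10. With 10 per group, 80% requires a difference of at least about 1.33 SDs of the change. Other models and readings move the figure in both directions. Because the plan gives no SD for the change, no correlation, no sidedness and no effect scale, the actual power for Vytorin against placebo is unknown. The 0.8 is therefore unsupported for that comparison, not shown to be missed at every SD. This should be corrected before the power statement is relied on.

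**What to change.** Make the sample size agree in Study Sample, Randomization and Data Analysis.

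If 20 in total stands, replace the power sentence with one for 10 per group that names the contrast, the test or model, the sidedness, the effect scale (25 points or 25% of 70) and the source of the SD, labelled as SD or S.E. Give power as conditional on that SD. Possible wording: *By a two-sample t-test on the change (two-sided alpha 0.05), 10 subjects per group give 80% power for Vytorin versus placebo only if the difference is at least about 1.33 SDs of the change.*

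If power is meant for the repeated measures ANOVA, state the residual SD, the time points used and the assumed within-subject correlation. If the powered contrast is the before-after change within the Vytorin group, say so, and state that the placebo comparison is not powered at 0.8. In either case, write 0.8 as power rather than as beta.

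**Cost.** If 20 in total is intended, the change is wording only, with no extra subjects, though the stated power for the placebo comparison becomes less favourable. If 20 per group is intended, 40 − 20 = 20 more subjects are needed, about 20 more weeks at the planned accrual of one per week.
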